2.5.5 Unscheduled visits

The determination of baselines and values at Month 6 and Month 12 for efficacy variables (measurements from the central laboratory only) is based on all measurements from both scheduled and unscheduled visits.

The determination of the last on-treatment value for safety parameters is also based on all assessments from both scheduled and unscheduled visits.

Unscheduled visit measurements of laboratory data, vital signs, will not be included in the by-visit summaries.

2.5.6 Pooling of centers for statistical analyses

Centers will be pooled to geographic US region and explored as a sensitivity analysis.

Note: this sensitivity analysis will concern US region only. It is not applicable to Canada due to low number of patients to be enrolled there, in comparison with US.

2.5.7 Statistical technical issues

Not applicable.

3 INTERIM ANALYSIS

One IA of primary composite endpoint is planned for the purpose of overwhelming efficacy to provide an early evaluation of Toujeo effectiveness, when approximately 1800 patients (54.2% information fraction of targeted sample size) have completed their 6-month (Day 180) visit.

Using a group sequential approach with a Gamma (-3) alpha-spending function and an overall two-sided alpha-level of 0.05, the two-sided nominal significance level is 0.010 at IA, and 0.046 at final analysis.

If the targeted sample size (1800) cannot be reached, it could be considered to include a lower number of patients, however not below 1700. In this case, the nominal significance level to be spent at interim and at final 6-month analyses would be recalculated accordingly before the database lock for IA.

Overwhelming efficacy will be shown at IA if the efficacy boundary is met, ie, if the two-sided p-value for comparison of primary composite endpoint incidence is below 0.010, corresponding to an estimated difference of 5.8% in favor of Toujeo between percentages of patients reaching the primary composite endpoint.

The corresponding conditional power to show overwhelming efficacy at IA under the alternative hypothesis is of 45%.

For the IA, analyses will be performed by an independent statistician, external to the Sponsor. Results will be delivered directly to an independent Data Monitoring Committee (DMC) for review. a DMC meeting will be organized for this IA.

- Scenario 1: If overwhelming efficacy is shown:
 - The recruitment would be stopped (total sample size at that time estimated to be between 2600 and 3000 patients),
 - The patients already enrolled would continue the study as planned.
 - The results will be disclosed to the Sponsor and a communication plan to protect clinical data integrity is detailed in the DMC charter.
- Scenario 2: If overwhelming efficacy is not shown (probability of 55% under the alternative hypothesis):
 - The study would continue as planned, up to the final 6-month and 12-month analyses.
 - The Sponsor would not have access to any unblinded data.
 - No results would be communicated.

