1.3 DETERMINATION OF SAMPLE SIZE

1.3.1 Original sample size

At time of initial protocol, calculations to determine the sample size of 1635 patients per treatment group are based on superiority testing of the primary efficacy variable of the proportion of patients reaching individualized HbA1c target at Month 6 without a documented symptomatic (BG \leq 70 mg/dL) or severe hypoglycemic event at any time of day from baseline to Month 6, with the following assumptions:

- Individualized HbA1c target attainment per HEDIS criteria of $<8\%$ if older or presence of medical comorbidities, or otherwise $<7\%$,
- An absolute difference of 5.5% in favor of Toujeo in patients assigned a target HbA1c $<7\%$, assuming a 30.1% rate in the Toujeo arm, based on data from the EDITION 3 study,
- An absolute difference of 5.4% in favor of Toujeo in patients assigned a target HbA1c $<8\%$, assuming a 55.8% rate in the Toujeo arm, based on data from the EDITION 3 study,
- An absolute overall (weighted average) difference of 5.5% in favor of Toujeo for all patients combined, assuming that 70% of the study patients would have a target HbA1c $<7\%$, and 30% would have a target HbA1c $<8\%$, based on data from a commercially available database,
- A maximum overall response rate of 33% in the comparator basal insulins arm,
- A 2-sided chi-squared test at the 5% significance level, with 90% power,
- All patients will be eligible for the primary endpoint analysis.

The assumptions are based on data from the EDITION program.

As a logistic regression model will be used for the primary analysis of the composite endpoint of individualized HbA1c target attainment without hypoglycemia, it is anticipated that the power will be higher due to reduced estimate variability compared with the chi-square test. Calculations were made using nQuery Advisor 6.01.

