1.3.2 Sample size for Interim Analysis

One interim analysis (IA) was added per Clinical Trial Protocol Amendment No. 01, for the purpose of efficacy to provide an early evaluation of Toujeo effectiveness, when 1800 randomized patients (54.2% information fraction of targeted sample size) have completed their 6-month (Day 180) visit.

Due to the addition of the IA the sample size will be increased to 1662 patients per treatment group (total of 3324 patients). The calculation takes into account one IA using a group sequential approach with an efficacy boundary based on a gamma (-3) alpha spending function, and an overall two-sided alpha-level of 0.05, the two-sided nominal significance level is 0.010 at IA, and 0.046 at final analysis.

The total sample size calculation of 3324 is based on the assumption of a maximum of a 33% overall (weighted average) response rate with Lantus, and at least a 5.5% increase in response rate with Toujeo, and assumes an overall 2-sided test with alpha-level 0.05 with an IA performed on 1800 patients followed 6 months.

Overwhelming efficacy will be shown at IA if the efficacy boundary is met, ie, if the two-sided p-value for comparison of primary composite endpoint incidence is below 0.010, with a difference in favor of Toujeo between percentages of patients reaching the primary composite endpoint. The corresponding power to show overwhelming efficacy at IA under the alternative hypothesis is of 45%.

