1.4 STUDY PLAN

[figure not shown]
The study will be a randomized, controlled, open label parallel group real world trial.

It will include a 6 month treatment period ending in assessment of the primary and secondary endpoints followed by a 6 month extension period for assessment of certain additional endpoints.

There will be three database locks:

- One at interim 6-month analysis,
- One at 6 months, once the last randomized patient has had an opportunity to complete 6 months of treatment,
- And one at 12 months.

Figure 1 - Graphical study design

R : Randomization

Cs and C180 : Clinical exam including vital signs: weight, height, systolic and diastolic blood pressure, heart rate as well as comprehensive physical exam

Ls: Hemoglobin A1c, fasting plasma glucose, serum creatinine, serum liver function tests including AST, ALT, total bilirubin, and alkaline phosphatase, serum pregnancy test for women of childbearing potential

L180: Hemoglobin A1c, fasting plasma glucose, serum pregnancy test for women of childbearing potential

L360: Hemoglobin A1c, fasting plasma glucose, serum pregnancy test for women of childbearing potential

Ps: DTSQ, Hypoglycemia Patient Questionnaire

P180 and P360: DTSQ, Hypoglycemia Patient Questionnaire, Patient GES, Provider GES

Table 2 - Study flow chart

VISIT	Screening	Treatment Period				
	1	2	3	4		
WEEK	-1	0	26 ±4	52 ±4		
DAY	-7	1 ±7	45	90	180 ±30	360 ±30
Informed Consent	X					
Inclusion/Exclusion Criteria	X					
Patient Demography	X					
Medical/Surgical History	X					
Prior Medication History	X					
Physical Examination	X			X		X
Vital Signs (including body weight)	X			X		X
DTSQs	X	X		X		X
DTSQc						X
Hypoglycemia Patient Questionnaire	X	X		X		X
Patient activation measure (PAM)	X					
Patient: GES				X		X
Provider: GES				X		X
Randomization		X				
IVRS call	X	X		X		X

		Screening	Treatment Period				
VISIT		1	2	3	4		
WEEK		-1	0	26 ±4	52 ±4		
DAY		-7	1 ±7	45	90	180 ±30	360 ±30
Treatment:	Dispensation of investigational medicinal product (IMP)		X				
	Concomitant Medication	X	X	X	X		
	Compliance			X	X		
	Insulin Pen Instruction		X				
	BG meter dispensing and training		X				
	E-diary dispensing and training		X				
	Offer to Enroll in PSP		X				
	Insulin dose				X	X	
Safety:	AE/serious adverse event (SAE) recording	X	X	X	X		
	Diary Reviews at visits		X	X	X		
	Hypoglycemia review of electronic source ^a			X	X		
Laboratory Testing:	HbA1c	X			X	X	
	FPG	X			X	X	
	Serum creatinine	X					

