1.5 MODIFICATIONS TO THE STATISTICAL SECTION OF THE PROTOCOL

In the protocol (1) Section 11.4.2, Analyses of efficacy endpoints, defines the analysis of HbA1c endpoints (change from baseline to 6 months) and self-reported satisfaction score using a mixed-effect model with repeated measures (MMRM) approach under the missing at random (MAR) framework, using an adequate contrast at Month 6. Since at the time of the 6 month database lock, only baseline and 6 month HbA1c data are available, an analysis of covariance (ANCOVA) will be performed at time of 6 month database lock and a MMRM at time of 12 month database lock.

In the protocol (1) Section 11.4.2, Analysis of primary efficacy endpoint(s), exploratory analysis for primary endpoint was modified. The Predictive Enrichment method is replaced by Subgroup Identification Based on Difference Effect Search (SIDES). The rationale is that the predictive enrichment procedure does not adjust for multiplicity. Additionally, the definition of subgroups is based on a score, defined as a function of multiple covariates, which makes difficult the clinical interpretation. On the other side, SIDES method uses fewer covariates (ie, 2 or 3 covariates), that is easier to interpret from a clinical point of view. Additionally, SIDES corrects for multiplicity.

As mentioned in Clinical Trial Protocol Amendment No. 01, an IA is planned when 1800 patients have completed their 6 month visit. The calculation takes into account one IA using a group sequential approach with an efficacy boundary based on a gamma (-3) alpha spending function.

The cut-off date for the IA is the date when 1800 patients have completed their 6 month visit.

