4 DATABASE LOCK

The database is planned to be locked at approximately 2 months after last patient last visit.

Prior to the final analysis of the 12 months, database will be locked:

- For the need of IA, when the 1800 patients have completed their 6-month visit, and their data have been cleaned and reconciled,
- At 6 months, when 6-month efficacy and safety data are available for all patients.

For the 6-months analysis, efficacy and safety data will be summarized and analyzed. Those CRF forms, which are not related to any specific study visits, will not be locked until the end of 12 months.

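### Does the interim analysis leave out patients who withdraw from the study before Day 180?

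*SAP*

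**What the plan says.** Four places in the SAP describe the interim patients. Section 3 times the analysis "when approximately 1800 patients (54.2% information fraction of targeted sample size) have completed their 6-month (Day 180) visit". Section 1.5 turns the same count into a calendar date: "The cut-off date for the IA is the date when 1800 patients have completed their 6 month visit". Section 4 locks the interim database "when the 1800 patients have completed their 6-month visit, and their data have been cleaned and reconciled". Section 1.3.2 bases the sample size on an overall test "with alpha-level 0.05 with an IA performed on 1800 patients followed 6 months". Section 3 also allows a smaller interim: "it could be considered to include a lower number of patients, however not below 1700".

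The scoring rules are elsewhere. SAP 2.4.4.1 places the primary analysis on the intention-to-treat population, gives the interim and final significance levels together, and treats a missing 6-month HbA1c as target not reached. SAP 2.5.2 scores a premature end of study in the first 6 months as a failure on every composite endpoint for that period. SAP 2.3.1 defines intention-to-treat as all randomized patients.

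For the 6-month lock, SAP 1.4 uses opportunity wording: "One at 6 months, once the last randomized patient has had an opportunity to complete 6 months of treatment". No such wording is attached to the interim lock.

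**The concern.** The scoring rules say how a patient counts, not who is in the interim set. Intention-to-treat cannot be applied literally at that point. SAP 3 expects 2600 to 3000 patients to have been enrolled by then, and scoring those not yet due at Day 180 as failures would not fit 1800 patients or 54.2% information. The interim set must therefore be a subset, and its membership rule is not written down. If 1800 were both the number of attenders and the denominator, patients who left before Day 180 would drop out of the interim comparison and return as failures in the final one.

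The interim would then estimate response among attenders. In an open-label trial with different support programmes by arm, study withdrawal could differ, and the comparison could shift either way. Crossing the boundary discloses results to the sponsor and, under SAP 3, stops recruitment.

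**Working it through.** **1. The plan's own figures.** Inputs: comparator rate 33% and difference 5.5 points, so 38.5% on Toujeo (SAP 1.3.1); 1:1 allocation, so 900 per arm; two-sided 0.010, so z = 2.576; total 3324.

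- Information fraction: 1800/3324 = 0.5415, or 54.2%.
- SE = √(0.385×0.615/900 + 0.33×0.67/900) = 0.02256.
- Boundary: 2.576 × 0.02256 = 0.0581. SAP 3 says "corresponding to an estimated difference of 5.8% in favor of Toujeo between percentages of patients reaching the primary composite endpoint".
- Power: P(Z > (0.0581 − 0.055)/0.02256) = P(Z > 0.137) = 44.5%. The SAP says 45%.

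These figures do not favour a completers-only reading. The planning assumes no loss ("All patients will be eligible for the primary endpoint analysis"). With no loss, patients who attended and patients who were due are the same people, so the match with 1800 cannot tell the readings apart.

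**2. How visit wording is used elsewhere.** The protocol synopsis times the final 6-month analysis by all 3324 randomized patients having had their 6-month visit. SAP 4 times the 6-month lock by 6-month data being available for everyone. Taken literally, both would require full attendance, yet the final analysis is explicitly intention-to-treat with leavers as failures. In those places visit completion is a timing statement. SAP 1.5 uses it the same way for the interim, to fix a cut-off date. The 6-month completer population in SAP 2.2 is a disposition category; no efficacy analysis is assigned to it.

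**3. Visit count as timing trigger.** Assume withdrawal w in both arms (the documents give no rate). The set is 1800 attenders plus the leavers of the same cohort, n = 1800/(1 − w), with rates 38.5% and 33%. Overall alpha is the two-sided probability of crossing at either look with the stated 0.010 and 0.046, using a bivariate normal with correlation √(n/3324).

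| w | n | n/3324 | Boundary (points) | Interim power | Overall alpha |
|---|---|---|---|---|---|
| 0% | 1800 | 54.2% | 5.8 | 45% | 0.0503 |
| 5% | 1895 | 57.0% | 5.7 | 47% | 0.0500 |
| 10% | 2000 | 60.2% | 5.5 | 50% | 0.0496 |
| 15% | 2118 | 63.7% | 5.4 | 53% | 0.0492 |
| 20% | 2250 | 67.7% | 5.2 | 56% | 0.0487 |

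Keeping leavers does not raise the type I error. The 0.0503 in the first row comes from the stated nominal levels (exact Gamma(−3) spending at 54.2% gives 0.0107 and 0.0453) and has nothing to do with who is in the set.

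**4. Completers only (the feared reading).** Observed rate = all-patient rate/(1 − withdrawal), 900 attenders per arm, same formulas. The null uses 33% in both arms.

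| Withdrawal, Toujeo / comparator | Crossing with no difference | Power |
|---|---|---|
| 5% / 5% | 0.5% | 49% |
| 20% / 20% | 0.5% | 64% |
| 12% / 10% | 1.4% | 69% |
| 15% / 10% | 5.1% | 88% |
| 10% / 12% | 0.2% | 39% |
| 10% / 15% | 0.02% | 19% |

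Example, 12% against 10% under the null: 0.33/0.88 = 0.3750, 0.33/0.90 = 0.3667, difference 0.0083, SE 0.02277, boundary 0.0586; P(Z > (0.0586 − 0.0083)/0.02277) = 1.4%.

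Equal withdrawal leaves false crossing at 0.5%. It moves only when withdrawal differs by arm and attendance is used to select patients.

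**The case for a change.** The strongest case for a change is that the scoring rules cannot select the set. SAP 2.3 fixes the efficacy population only at the 6-month lock; SAP 2.2 defines completing the period by attendance at Visit 3; SAP 3 treats 1800 as the number included; and only the 6-month lock has opportunity wording. An external statistician could cut the data on attendance in good faith, and the 15% against 10% row shows a tenfold rise in false crossing.

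It is true that no sentence states the cut. The inference to a completers-only set does not hold. That set would make the SAP's own rule on leavers inoperative at the interim, although 2.4.4.1 names the interim test and the intention-to-treat population together. The natural set under those rules is everyone whose 6-month outcome is due by the cut-off, with leavers as failures.

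The exposed group is also narrower than it looks. Patients who stop insulin are asked back at Day 180 (protocol 10.3.3), and attenders with no HbA1c already count as failures. One practical point remains: with leavers added, n can exceed 1800, and the SAP mentions recalculating the levels only for a smaller interim. The alpha column above shows that leaving them unchanged is harmless.

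**Conclusion.** This is a missing detail that an analyst applying SAP 2.4.4.1 and 2.5.2 would fill correctly, so no change follows. As written, the plan shows no bias and no loss of error control from this source. On the timing reading, the effect is an interim power of 47% to 56% instead of 45% for assumed withdrawal of 5% to 20%, with overall alpha no higher than at 1800. The larger shifts (1.4% or 5.1% false crossing, or power down to 19%) require attendance to be misused as a selector; the changes in false crossing also require withdrawal to differ by arm, at rates the documents do not give.

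Even then the damage is limited: enrolled patients continue, and protocol 6.4.1 has the whole study population analysed whatever the interim shows. A sentence naming the cut would only record what the existing rules already produce. The calculations take the 38.5% and 33% planning rates as all-patient rates. The DMC charter was not available and may already state the cut.

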| STATISTICAL CONSIDERATIONS | 
Sample Size Determination:
 
An original sample size of 1635 patients per treatment arm would provide at least 90% power to demonstrate superiority with an absolute difference of at least 5.5% in favor of Toujeo versus comparator basal insulins in the proportion of patients reaching individualized HbA1c target at month 6 without a documented symptomatic ($BG \leq 70$ mg/dl) or severe hypoglycemic event from baseline to month 6, assuming 30% of patients enrolled have a target HbA1c <8 per HEDIS criteria due to being older or due to the presence of medical comorbidities, and the remaining 70% having a target HbA1c $<7\%$.
 
Due to the addition of the interim analysis the sample size will be increased to a total of 3324 patients (1662 patients per treatment group). The calculation takes into account one interim analysis using a group sequential approach with an efficacy boundary based on a gamma (-3) alpha spending function.
 
The number of patients meeting each of these criteria will be monitored via demographic and ICD-9 data to avoid significant deviations from the assumptions above.
 
The total sample size calculation of 3324 is based on the assumption of a maximum of a 33% overall (weighted average) response rate with Lantus, and at least a 5.5% increase in response rate with Toujeo, and assumes an overall 2-sided test with alpha-level 0.05 with an interim analysis performed on 1800 patients followed 6 months.
 
Analysis Populations:
 
The primary analysis will be performed on the Intent-To-Treat (ITT) population, which will comprise all randomized patients, irrespective of the treatment actually being received at the time of analysis.
 
Safety will be assessed on an as-treated population, defined as all randomized patients who actually received at least 1 dose or part of a dose of IMP, analyzed according to the treatment actually received.
 
Primary Analysis:
 
The proportion of patients reaching individualized HbA1c target at 6 months without documented symptomatic ($BG \leq 70$ mg/dl) or severe hypoglycemia will be compared between treatment groups using a logistic model with log link, adjusting for individualized HbA1c target ($<8\%/<7\%$) and other stratification factors used at randomization: SU use ever (y/n), GLP-1 RA use ever (y/n), and baseline HbA1c (as continuous). As a sensitivity analysis, a multivariate analysis will be performed, adding the following baseline characteristics BMI, Patient Activation Measure (PAM) as an assessment of patient engagement, duration of diabetes and age.
 
One interim analysis is planned for the purpose of overwhelming efficacy on the primary composite endpoint when 1800 patients have been randomized and completed their 6-month visit (54.2% information fraction), using a two-sided nominal significance level of 0.010 based on a Gamma (-3) alpha-spending function.
 
The final 6-month analysis will be conducted when all randomized patients (3324) have performed their 6-month visit. The two-sided nominal significance level to be used at this final 6-month analysis is 0.046.
 
Patients with missing HbA1c data at 6 months will be regarded as not having reached HbA1c target.
 |

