6.4 STUDY COMMITTEES

6.4.1 Data Monitoring Committee

An independent DMC will be in charge of reviewing the unblinded efficacy results of the interim analysis. The DMC will give appropriate recommendations to the Sponsor on whether overwhelming efficacy is reached or not for the primary composite endpoint. The DMC may make recommendations regarding any measures that may be required for ensuring the integrity of the study results during the execution of its primary mission including assessing the risk benefit.

Overwhelming efficacy will be shown if the p-value of the superiority test for comparison of Toujeo and comparator basal insulins on the primary endpoint is below 0.010 with a higher proportion of patients reaching the primary endpoint in the Toujeo group.

The corresponding power to show overwhelming efficacy at interim analysis under the alternative hypothesis is of 45%.

If overwhelming efficacy is not shown (probability of 55% under the alternative hypothesis) the Sponsor would not see the unblinded data, and no results would be communicated. If

overwhelming efficacy is shown (probability of 45% under the alternative hypothesis) the Sponsor would see the data, and results would be communicated in agreement with the DMC. It could be considered to stop the recruitment (total sample size at that time estimated to be between 2600-3000 patients). However, study participation for patients already recruited would continue as planned. In either case (superiority achieved at interim or not), the study will continue up to month 6 and up to month 12 as planned, with analyses performed on whole study population.

The DMC consists of 3 members 2 of whom are clinicians with expertise in diabetology and one biostatistician. Members of the DMC are independent of those performing these studies, being neither Investigators nor employees of the Sponsor and without conflict of interest regarding study outcomes. For details, please refer to the DMC charter.

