11.4.2 Analyses of efficacy endpoints

11.4.2.1 Analysis of primary efficacy endpoint(s)

A superiority test will be performed at interim analysis (2-sided, $\alpha=0.010$) and at final 6-month analysis (2-sided, $\alpha=0.046$) to compare the proportion of patients reaching individualized HbA1c target at 6 months without documented symptomatic ($BG \leq 70$ mg/dl) or severe hypoglycemia between treatment groups using a logistic model with log link, adjusting for HbA1c target and other stratification factors used at randomization: SU use ever (y/n), GLP-1 RA

use ever (y/n), and baseline HbA1c (as continuous). In a sensitivity analysis a multivariate analysis will be performed, adding the following baseline characteristics such as BMI, Patient Activation Measure (PAM) as an assessment of patient engagement, duration of diabetes and age.

Patients with missing HbA1c data at 6 months will be regarded as not having reached HbA1c target.

In order to examine the consistency of this analysis, the individual components of HbA1c target attainment and absence of any documented symptomatic ($BG \leq 70$ mg/dl) or severe hypoglycemia will also be evaluated. Each individual component will be compared between treatment groups using logistic regression, adjusting for randomization strata and other baseline characteristics as clinically appropriate.

Further, a predictive subgroup identification method will be employed to identify subgroups of potential responders.

Analyses of secondary efficacy endpoints ([Section 9.2.1](#)).

Persistence:

- Treatment persistence will be determined based on vendor database that would be responsible for managing and administration of the study drugs (Toujeo, Lantus, Levemir) from the vendor database administering the study drugs, information on prescription fill date, quantity dispensed, days of supply, number of units dispensed, prescription refill dates will be obtained in estimation of treatment persistence and discontinuation.
- In addition, for US patients, a medication possession ratio will be assessed for patients based on number of days that patients had possession of study drug based on prescription date and days of supply. A MPR of 80% would be indicative of patients being persistent on study medication. Those not persistent will be considered discontinued on their study medication.
- Treatment persistence will be summarized descriptively (N, Mean, SD, Median, Min, and Max).

Efficacy Endpoints:

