11.5 INTERIM ANALYSIS

One interim analysis is planned for the purpose of efficacy to provide an early evaluation of Toujeo effectiveness, when approximately 1800 patients (54.2% information fraction of targeted sample size) have completed their 6-month (Day 180) visit.

Using a group sequential approach with a Gamma(-3) alpha-spending function and an overall two-sided alpha-level of 0.05, the two-sided nominal significance level is 0.010 at interim analysis, and 0.046 at final analysis.

If the targeted sample size (1800) cannot be reached, it could be considered to include a lower number of patients, however not below 1700. In this case, the nominal significance level to be spent at interim and at final 6-month analyses would be recalculated accordingly before the database lock for IA.

Overwhelming efficacy will be shown at interim analysis if the efficacy boundary is met, ie, if the two-sided p-value for comparison of primary composite endpoint incidence is below 0.010, with a difference in favor of Toujeo between percentages of patients reaching the primary composite endpoint. The corresponding power to show overwhelming efficacy at interim analysis under the alternative hypothesis is of 45%.

Scenario 1: If overwhelming efficacy is shown:

- The recruitment would be stopped (total sample size at that time estimated to be between 2600-3000 patients),
- The patients already enrolled would continue the study as planned,
- The results will be disclosed to the Sponsor and a communication plan to protect clinical data integrity is detailed in the DMC charter.

Scenario 2: If overwhelming efficacy is not shown:

- The study would continue as planned
- The Sponsor would not have access to any unblinded data,
- No results would be communicated.

For the interim analysis, analyses will be performed by an independent statistician external to the Sponsor. Results will be delivered directly to the independent Data Monitoring Committee for review.

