2.4.4.1 Analysis of primary efficacy endpoint

The primary efficacy analysis will be performed on the ITT population, using all post-baseline HbA1c data available and hypoglycemia events collected on the 6-month randomized period, regardless of IMP discontinuation.

The primary efficacy endpoint: proportion of patients reaching individualized HbA1c target at 6 months without documented symptomatic ($BG \leq 70$ mg/dL) hypoglycemia will be analyzed using a logistic regression model, adjusting for HbA1c target and other stratification factors used at randomization: SU use (y/n), GLP-1 RA use (y/n) and baseline HbA1c (as continuous). a superiority test will be performed to compare this proportion between treatment groups at IA

(2-sided, alpha = 0.010) and at final 6-month analysis (2-sided, alpha = 0.046). Treatment difference will be assessed by odds ratios and CIs. For the primary efficacy analysis, the randomization strata from IVRS will be used.

Patients with missing HbA1c data at 6 months will be regarded as not having reached HbA1c target. In order to examine the consistency of this analysis, the individual components of HbA1c target attainment and absence of any documented symptomatic (BG ≤70 mg/dL) or severe hypoglycemia will also be evaluated. Each individual component (HbA1c target attainment at 6 month, or absence of any documented symptomatic [BG ≤70 mg/dL] or severe hypoglycemia), will be compared between treatment groups, respectively, using same logistic regression model as the primary efficacy analysis.

Sensitivity analyses

The sensitivity analyses of primary efficacy endpoint will be performed at time of 6-month database lock.

- **On-treatment sensitivity analysis.**

A sensitivity analysis for the primary efficacy endpoint will be performed on the 6-month on-treatment period, as defined in [Section 2.1.3](#).

- **Multivariate analysis.**

As a sensitivity analysis, a multivariate analysis will be performed, adding the following baseline covariates in the model: BMI, duration of diabetes, baseline PAM score, hypoglycemic history and age. a backward selection procedure at 0.10 level will be used get the final model with these exploratory factors. Treatment effect will be re-evaluated based on the final model.

Country (USA/Canada) and US region effect systematic group difference will be explored.

- **Sensitivity analysis of primary efficacy endpoint with randomization strata from e-CRF.**

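### The stated significance levels 0.010 (interim) and 0.046 (final) are not the Gamma(-3) levels at 1800 of 3324 patients, and together they spend 0.0503 rather than 0.05

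*SAP*

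**What the plan says.** The design is described in Protocol section 11.5 and SAP sections 1.3.2 and 3. It has one interim look for efficacy at about 1800 of 3324 patients (54.2% information), Gamma(-3) spending and an overall two-sided alpha of 0.05.

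The resulting levels appear throughout both documents:

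- SAP section 3: "the two-sided nominal significance level is 0.010 at IA, and 0.046 at final analysis". SAP section 1.3.2 gives the same pair.
- Protocol section 11.5: "the two-sided nominal significance level is 0.010 at interim analysis, and 0.046 at final analysis".
- Protocol synopsis, statistical considerations: the interim is tested "using a two-sided nominal significance level of 0.010 based on a Gamma (-3) alpha-spending function", and then "The two-sided nominal significance level to be used at this final 6-month analysis is 0.046".
- Protocol section 6.4.1: overwhelming efficacy is shown if the p-value "is below 0.010 with a higher proportion of patients reaching the primary endpoint in the Toujeo group".
- Protocol section 11.4.2.1 and SAP section 2.4.4.1 carry the pair into the primary test; the SAP wording is "2-sided, alpha = 0.010) and at final 6-month analysis (2-sided, alpha = 0.046".

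Neither document gives more decimals or explains any rounding. Both provide for recalculating the levels before the interim database lock, but only if fewer than 1800 patients are available (not below 1700).

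**The concern.** The spending function, overall alpha, interim size and final size are all stated, so the two levels are fixed by arithmetic. The stated levels differ from the computed ones in the third decimal, in opposite directions. The question is whether the pair still holds the promised 5%.

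The primary endpoint carries the only confirmatory test; the secondary endpoints are declared exploratory with no multiplicity adjustment (Protocol section 9.2.1, SAP section 2.4.4.3). A final p-value between 0.0457 and 0.046 would be declared significant without 5% control, even with the strict 0.010 kept at the interim. With 0.0107 at the interim, the limit is 0.0453.

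The levels would also not join up. If the interim had 1790 patients, the recalculation clause would give 0.0106/0.0453, while 1800 patients would use 0.010/0.046.

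**Working it through.** **Inputs**

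- Overall two-sided alpha 0.05 and Gamma(-3) spending: Protocol 11.5, SAP 3.
- Interim N = 1800 and final N = 3324 (1662 per arm): SAP 1.3.2.
- Planning rates 33% and 38.5% (33% plus 5.5 points): Protocol 11.1, SAP 1.3.1.

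**Related figures that reproduce**

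With 900 per arm at the interim, the standard error of the difference is √[(0.33×0.67 + 0.385×0.615)/900] = 0.02256. The two-sided 0.010 critical value is z = 2.576.

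- Boundary: 2.576 × 0.02256 = 5.81 points (SAP section 3 says 5.8%).
- Interim power: P(Z > 2.576 − 0.055/0.02256) = 44.5% (stated 45%).

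At 0.0107 these become 5.76 points and 45.5%. Both stated figures therefore fit either interim level.

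**Interim level under Gamma(-3)**

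The information fraction is t = 1800/3324 = 0.5415.

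α₁ = 0.05 × (e^{3t} − 1)/(e³ − 1) = 0.05 × (5.0761 − 1)/(20.0855 − 1) = 0.01068

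Using the rounded fraction 0.542 gives 0.01070, so rounding t does not matter.

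**Final level**

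Solve P(|Z₁| ≥ c₁ or |Z₂| ≥ c₂) = 0.05 with corr(Z₁, Z₂) = √t. With c₁ = 2.553, numerical integration gives c₂ = 2.002, a two-sided level of 0.0453. If exactly 0.010 is spent at the interim instead, the final level is 0.0457.

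**Overall two-sided error at an interim N of 1800**

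| Interim / final | Overall error |
|---|---|
| 0.010 / 0.046 (stated) | 0.05028 |
| 0.0107 / 0.0453 | 0.05002 |
| 0.0100 / 0.0457 | 0.0500 |
| 0.011 / 0.045 | 0.0499 |

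A simulation of 40 million pairs gave 0.0502 for the stated levels.

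**Does another interim size explain the stated pair?**

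| Interim N | Gamma(-3) interim | Gamma(-3) final | Overall error of 0.010/0.046 |
|---|---|---|---|
| 1700 | 0.00953 | 0.04563 | 0.0506 |
| 1742 | 0.01000 | 0.04549 | 0.0505 |
| 1800 | 0.01068 | 0.04529 | 0.0503 |
| 1882 | 0.01170 | 0.04501 | 0.0500 |
| 2000 | 0.01331 | 0.04458 | 0.0496 |

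Both Gamma(-3) levels round to 0.010 and 0.046 only for an interim N of 1698 to 1739. The stated pair stops overspending at about N = 1882.

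**Consequence for the decision**

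With 1662 per arm the standard error is 0.016598 at the planning rates. The final boundary and overall power are:

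| Pair | Final boundary (points) | Overall power |
|---|---|---|
| 0.010 / 0.046 | 1.9954 × 1.6598 = 3.312 | 90.8% |
| 0.0107 / 0.0453 | 2.0019 × 1.6598 = 3.323 | 90.8% |
| 0.0100 / 0.0457 | 1.9982 × 1.6598 = 3.317 | 90.8% |

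The largest shift is 0.011 point, or 0.00011 × 1662 ≈ 0.2 of a responder.

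**The case against.** The strongest objection is materiality. The excess is 0.0003 two-sided, and about 0.0001 for a claim in favor of Toujeo (0.0251 instead of 0.025). The p-values come from a large-sample logistic test. As a comparison, the exact size of a pooled two-proportion test at nominal 0.05 with 1662 per arm runs from 0.0496 to 0.0501 over common response rates of 25% to 40%, an error of similar size. This stands, and it is why the point is minor.

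A second objection is that the pair could be a matter of displayed precision: 0.0107 cut to 0.010, the final level re-solved as 0.0457, then rounded to 0.046. That may be how it arose, although neither document says so. It does not rescue the pair, because rounding a final level up overspends, and the levels would then not be those of Gamma(-3) at 54.2%.

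A third objection is that the interim is set at approximately 1800. A lower N makes the overspend larger, although the recalculation clause covers that case. A higher N makes it smaller. The trigger is 1800 completed six-month visits (SAP 1.5 and 4), whereas the primary analysis is ITT, with missing HbA1c and early study withdrawal counted as failure (SAP 2.4.4.1 and 2.5.2). If early withdrawals enter the interim dataset, N exceeds 1800, and non-completion of 1 − 1800/1882 = 4.4% would remove the excess. The documents give no dropout rate, and the DMC charter, which was not available, may settle who is counted. This qualifies the figure of 0.0503 but does not make the stated levels correct for the stated design.

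**Conclusion.** The concern holds. For the design as written, Gamma(-3) gives 0.0107 and 0.0453. The stated 0.010 and 0.046 give an overall two-sided error of 0.0503, and the whole excess comes from the final level.

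The result assumes an interim N of exactly 1800, a final N of 3324, and the usual joint normal distribution of the two test statistics with correlation √t. It does not depend on the response rates; only the boundaries and power do.

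The severity is minor. No realistic conclusion would turn on the difference, but the documents attribute to the spending function levels that it does not produce.

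**What to change.** State the levels to four decimals in the Protocol synopsis and sections 6.4.1 (interim level only), 11.4.2.1 and 11.5, and in SAP sections 1.3.2, 2.4.4.1 and 3. Two pairs are suitable for an interim N of 1800:

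- **0.0100 / 0.0457**, declared as a deliberate choice of 0.0100 at the interim. Overall error is 0.0500, and the published interim threshold is unchanged.
- **0.0107 / 0.0453**, the Gamma(-3) levels. Overall error is 0.05002, the residue being four-decimal rounding.

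The first is the simpler change and holds 0.05 at the stated precision.

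Extend the recalculation clause so that both levels are recomputed before the interim lock from the actual information fraction, whether the interim N is below or above 1800. Add one sentence saying who counts in that N, so that the 1800 visit completers are reconciled with the ITT rule that missing means failure. If early withdrawals are counted, recompute both levels for the larger N.

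The cost is wording. The final threshold becomes very slightly stricter, power stays at about 91%, and sample size and data collection do not change.
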